*Improving phenotyping for salt-sensitivity:* At the present time, describing the salt-sensitive phenotype in humans requires BP measurement under conditions of high and low-sodium balance (i.e., conditions where sodium intake equals excretion) following one or more weeks of constant sodium intake (Chen et al. 2009), or

measuring the BP response to rapid dietary sodium loading then depletion with diuretics over a two-day inpatient protocol (Weinberger et al. 2001). Since the BP response to changes in sodium intake is normally distributed in the population, arbitrary thresholds for BP change are used to establish the salt-sensitive phenotype. Salt-sensitivity was originally defined as a change of ≥10% in mean BP between low- and high-sodium conditions; other studies have used thresholds of 3-10 mmHg change in mean or systolic BP. Whatever threshold is used, both sets of measurements are subject to random fluctuations in BP as well as random error in BP assessment that can reduce reproducibility. Automated 24-hour ambulatory BP monitoring can reduce this variance and is recommended by experts in the field (Elijovich et al. 2016). Nonetheless, due to the need to institute and maintain meticulously controlled diets as an outpatient or measure the inpatient BP response to physiological provocation, the salt-sensitive phenotype is challenging to define in clinical practice. As recently stated by the American Heart Association, a biomarker for salt-sensitivity is needed and "should emerge from... protocols that use arbitrary BP cutoffs to define the phenotype." Such a biomarker could then be "validated by [its] association with characteristics of the phenotype (Elijovich et al. 2016)."

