**Phase 1 study design:** Consented participants will have clinic BP measured at the screening visit and will enter a two-week usual diet period, during which antihypertensive medications, with the exception of calcium channel blockers, will be weaned off under [name] supervision and with guidance from daily home BP monitoring. During this time period, the participant will consume their usual diet. Potential subjects with ontreatment, resting, average systolic BP of > 160 mmHg at the screening visit will be excluded from further

participation, as will those with symptomatic hypertension or systolic BP of > 180 mmHg on more than one occasion during the ad-lib dietary period.

Following the usual diet period and the week 2 visit, participants will consume the DASH/SRD diet for 14 days each. This time period is sufficient to demonstrate changes in BP and arterial stiffness, which peak at 2 weeks after dietary sodium modification (Gates et al. 2004). In addition to in-clinic BP measurement, 24-hour ambulatory BP will be obtained at the end of each dietary sequence. We expect that the DASH/SRD will reduce BP across the cohort, but differentially on an individual basis (Sacks et al. 2001).

The salt-sensitive vs. salt-resistant phenotype will be defined as a change in 24-hour mean BP of ≥8 mmHg between control and DASH/SRD dietary segments (Castiglioni et al. 2011). Based on previous studies in patients with HTN, we expect that 30-50% of participants will be classified as salt-sensitive (Elijovich et al. 2016). The 24-hour ambulatory BP monitoring and 24-hour urinary collections will be used to provide an alternate definition of salt-sensitivity. Specifically, the quantitative Sodium Sensitivity Index will be calculated as the change in 24-hour mean BP divided by the change in 24-hour urinary sodium excretion between DASH/SRD and control diet periods (Castiglioni et al. 2011).

The *Phase 1* primary outcome is the cfPWV compared at the end of usual diet and DASH/SRD. This parameter was chosen because of its association with incident HF in community-dwelling elderly (Tsao et al. 2015) and its high sensitivity and specificity for HF in older adults with unexplained exertional dyspnea (Weber et al. 2013). Key secondary outcomes include ventricular diastolic function (k; ventricular stiffness) and systolic function (global longitudinal ventricular strain) and left atrial reservoir function (left atrial strain).

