Potential problems/alternative approaches: Despite our previous experience in collecting 24-hour BP and urinary data, it is possible that some attempts could be incomplete. If this occurs, the dietary intervention would be continued for an additional 24 hours to repeat the measurement. If despite these efforts, one or both of the 24-hour BP or urine collection are unacceptable in an individual, we would assign the salt-sensitive phenotype if clinic-measured mean BP is >5 mmHg higher following the control diet vs. the DASH/SRD segment; this threshold has been previously used to define salt-sensitivity in metabolic syndrome (Chen et al. 2009). This could affect the distribution of salt-sensitivity slightly, but we expect that few patients will have incomplete data and there will be no bias in missing data by underlying phenotype. The detectable effect size would increase based on the degree of imbalance between the number of subjects defined as salt-sensitive vs salt-resistant. In the event that this imbalance is as high as 70%:30%, the detectable effect size with >80% power would be 0.62 with a two-sided Type I error of 5%. If the distribution of salt-sensitivity is markedly different than expected, we would perform a secondary analysis using the median value or other appropriate cutpoint of the quantitative Sodium Sensitivity Index (Castiglioni et al. 2011).

We do not expect substantial difficulty in obtaining cardiovascular measures; [name] is evaluating all proposed echocardiographic parameters in four ongoing studies, including two NIH-funded studies using DASH/SRD as the intervention. A major focus of [name] NIH/NHLBI K23 award has been non-invasive vascular assessment. In the event that one or more of the cardiovascular measures cannot be obtained, multiple imputation methods will be used. In the course of studies conducted by [name] team, >120 subjects have completed dietary interventions, involving provided food and/or dietary counseling, lasting three weeks to four months. Adherence to provided meals has been excellent overall, but it is likely that some non-adherence will occur. The primary analysis will be intent-to-treat; if any subjects are severely nonadherent (via 24-hour urinary sodium or food diary review) we would do secondary analyses excluding these participants.

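### The clinic-BP fallback for salt-sensitivity also fires when only the 24-hour urine fails, overriding a valid 24-hour BP classification with a lower cut-off

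*Protocol*

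**What the plan says.** Protocol, Phase 1 study design: the phenotype is "defined as a change in 24-hour mean BP of ≥8 mmHg between control and DASH/SRD dietary segments". A second, quantitative measure follows: "The 24-hour ambulatory BP monitoring and 24-hour urinary collections will be used to provide an alternate definition of salt-sensitivity". This is the Sodium Sensitivity Index, "the change in 24-hour mean BP divided by the change in 24-hour urinary sodium excretion". Urine is needed only for that index.

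Protocol, Study procedures: the two measurements have separate acceptability tests. BP recordings are judged against published norms and urine completeness against creatinine excretion. One can fail while the other is sound.

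Protocol, Study phase 1, Potential problems/alternative approaches: a failed attempt is repeated after a further 24 hours on the diet. After that, if "one or both of the 24-hour BP or urine collection are unacceptable in an individual, we would assign the salt-sensitive phenotype" when "clinic-measured mean BP is >5 mmHg higher following the control diet vs. the DASH/SRD segment". No sentence keeps the ambulatory classification when urine alone has failed. The same paragraph expects few incomplete cases and only a slight effect on the distribution of the phenotype.

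Protocol, Improving phenotyping for salt-sensitivity: on the choice of instrument, "Automated 24-hour ambulatory BP monitoring can reduce this variance and is recommended by experts in the field".

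SAP, Phase 1 description: salt-sensitivity is a fall in 24-hour ambulatory mean arterial pressure from week 2 to week 4. The SAP gives no cut-off, no urine condition and no clinic-BP substitute.

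**The concern.** The fallback is triggered by a sample that the definition it replaces does not use. Take a participant with two acceptable ambulatory recordings, a 24-hour fall of 3 mmHg, a clinic fall of 6 mmHg and one incomplete urine collection. The main rule says salt-resistant; the fallback says salt-sensitive. With a 24-hour fall of 9 and a clinic fall of 4, the label flips the other way. In both cases the measurement that the protocol itself prefers is available and is set aside.

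The phenotype is the factor in the protocol's Phase 1 interaction test, the grouping for its Phase 2 comparison of left ventricular mass index (LVMI), and a reference variable in Aim 3. Needless misclassification pulls the two groups together and makes the split depend partly on who completed a urine collection.

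**Working it through.** **The plan's own figure.** The only computable number in the fallback paragraph is the detectable effect of 0.62 at a 70:30 split with more than 80% power. A two-sample t test with 70 vs 30 participants and two-sided alpha 0.05 has power 0.803 at 0.62, so it reproduces with N = 100. The point here does not depend on it.

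**The rules side by side.**

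| | Main rule | Sodium Sensitivity Index | Fallback |
|---|---|---|---|
| Needs 24-hour BP | yes | yes | no |
| Needs 24-hour urine | no | yes | no |
| Instrument | ambulatory | ambulatory + urine | clinic |
| Cut-off | ≥8 mmHg | quantitative | >5 mmHg |
| Fires when | default | alternate definition | BP or urine fails |

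A urine failure blocks the index. It does not block the main rule. Reading the trigger as referring to the two diet periods rather than the two measurements changes nothing, because urine is still listed.

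**Effect of the cut-off alone.** Assume that the 24-hour change is normal with SD σ = 6, 8 or 10 mmHg (assumption) and mean μ set so that 30, 40 or 50% reach 8 mmHg (the protocol expects 30-50%). If clinic and 24-hour changes agreed perfectly, those between 5 and 8 mmHg would switch:

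share switching = Φ((8−μ)/σ) − Φ((5−μ)/σ)

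For 40% and σ = 8: μ = 8 − 8 × 0.2533 = 5.97, and the share is 0.600 − 0.452 = 0.148. Over the grid it is 0.11-0.20, all from resistant to sensitive.

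**Adding clinic error.** Let the clinic change equal the 24-hour change plus error with SD 0, 5 or 8 mmHg (assumption; 2,000,000 draws per cell). The two rules then disagree in 11-32% of people, and the salt-sensitive share among those affected moves from 30-50% to about 41-69%. With error SD 5-8, 21-42% of resistant participants become sensitive and 6-21% of sensitive participants become resistant.

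**A second set of assumptions.** The pilot (24-hour mean BP 89 to 84 mmHg, p = 0.04, n = 13) implies an SD of change of 5/2.303 × √13 = 7.83. Take a mean change of 5, true SD 6.3-7, 24-hour noise SD 3.6-4.8 and clinic noise SD 6-10 (the SD and noise ranges are assumptions). The rules then disagree in 28-37%: 22-26% of people move from resistant to sensitive and 7-11% the other way.

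**Number affected.** The documents give no rate of urine-only failure. If 5-15 participants had one (assumption), the first grid gives 0.11 × 5 = 0.6 to 0.32 × 15 = 4.8, roughly 1-5 changed labels. The top of the second set gives 0.37 × 15 = 5.6.

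**Effect on the contrast.** Under the second set of assumptions, if 3-10% of participants are classified by the fallback, the sensitive-minus-resistant difference in true BP change shrinks by about 1-5%.

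**The case against.** The best defence is that little may come of it. The fallback applies only after a repeat attempt, the protocol expects few such cases and concedes a slight shift, and it plans a secondary analysis if the phenotype split is far from expected. All of this limits the size. None of it explains why a failed urine collection should displace a valid ambulatory result. Nor does the expectation that missingness is unrelated to phenotype help: the cut-off itself drops, so relabelling leans toward salt-sensitive even when urine failures are random.

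The 5 mmHg threshold has a cited precedent in metabolic syndrome, and the protocol calls all such thresholds arbitrary. That supports a fallback when ambulatory BP is missing, not an override when it is present.

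A reader might go further than the documents allow in three ways:

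- **That ten or more participants, or a large part of the contrast, are at risk.** This needs a high assumed failure rate. It also must not count people whose ambulatory BP failed too, since for them the fallback is appropriate.
- **That the clinic rule is wrong in about 26-34% of people, against 14-19% for the 24-hour rule.** The second set of assumptions does give those figures, but they score a >5 rule against a true ≥8 status, so part of the gap is only the difference in cut-off. The pilot inputs also come from 13 patients with heart failure, whom this trial excludes.
- **That the SAP's results are affected.** The SAP contains no fallback, and its Phase 2 LVMI comparison is between WHEELS groups, not phenotypes. Nothing shows that the fallback was ever applied.

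**Conclusion.** The point stands as a flaw in the protocol's wording. Followed literally, the fallback replaces a valid 24-hour BP classification because of a sample that the classification does not use. That the trigger includes urine and the main definition does not is certain from the text.

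The size is uncertain and probably small: about 11-37% of urine-only failures would change label, mainly toward salt-sensitive, or roughly 1-5 participants if 5-15 had such failures. The noise levels and the failure count are assumptions. The 1-5% shrinkage refers to true BP change and was not computed for pulse wave velocity or LVMI.

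The reach is the protocol's Phase 1 interaction test, the protocol's Phase 2 LVMI comparison by phenotype, and Aim 3. For the SAP, the gap is silence: it does not say how a urine-only failure, or a failed BP recording, is classified. The correction is worth making because it is cheap and removes a needless source of misclassification, not because the main conclusions are likely to turn on it.

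**What to change.** 1. In the protocol's Phase 1 section on potential problems, limit the clinic-BP fallback to participants whose 24-hour BP recording at Week 2 or Week 4 is unacceptable.
2. For a urine-only failure, keep the 24-hour BP classification and set only the Sodium Sensitivity Index to missing.
3. State the same rule in the SAP.
4. If the fallback was applied, re-derive the phenotype for every participant it classified who has two valid 24-hour BP recordings, and report how many labels changed. If urine-only failures were in practice left on the ambulatory classification, a sentence saying so closes the point.

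The cost is about one sentence in each document and, at most, one re-run of the classification and the analyses that use it. No new data are needed.

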**Phase 2 study design:** We will test our working hypotheses by providing motivational interviewing-based counseling to all participants and randomizing half to the WHEELS-I program, with both interventions described further below. The primary outcome of Aim 2 of this proposal, to be tested in Phase 2 of the protocol, is the intra- and inter-group mean change in DASH/SRD concordance score (Mellen et al. 2008) from the baseline value obtained at the beginning of the study. This score provides 1 point for fully meeting each of 9 DASH/SRD targets and 0.5 for meeting an intermediate level of each target (e.g. fiber 14.8 g and 9.5g/1000 kcal, respectively). The secondary dietary outcome is the group change in mean 24-hour urinary sodium excretion compared to baseline values. Other outcomes of interest are urinary potassium, microalbuminuria, and the nutrient composition from three day food diaries.

We will also test if DASH/SRD adoption differentially improves HFpEF-associated structural cardiovascular parameters in salt-sensitive vs. salt-resistant subjects (as they were defined by BP response in *Phase 1*). The primary cardiovascular outcome of *Phase 2* is the change from baseline (Week 2 visit) to 6 months in left ventricular mass index (LVMI, indexed to height2.7). This measure was chosen because LVMI is a strong risk factor for incident HF (Gottdiener et al. 2000), can decrease after 6 months of dietitian-counseled sodium restriction (Jula et al. 1994, Liebson et al. 1995), and is relevant to the pathophysiology of HFpEF (Melenovsky et al. 2007). Key secondary outcomes include cfPWV (see *Aim 1*), left atrial volume, indexed for body surface area (LAVI) (Melenovsky et al. 2015), and 24-hour mean BP.

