Phase 2 data collection: History and exam, questionnaires, blood tests, 24-hour BP and urine collections will be performed at months 1 and 6 of Phase 2 (see Study procedures above). Dietary concordance with DASH/SRD, the measure of exposure in Phase 2, will be assessed via Block Food Frequency Questionnaire and 24-hour urine sodium excretion at month 6, and 3-day food diaries immediately prior to the Month 1 and Month 6 visits. Arterial tonometry, echocardiography, SDF microscopy, and the mini-SBT will be performed at Month 6 of Phase 2 (see also Figures 7 and 8). Following Phase 2, participants will have follow-up after 6 months via telephone interview to assess cardiovascular events and vital status; subjects will be mailed a Food Frequency Questionnaire to evaluate persistence of dietary patterns after study participation; and there may be an optional in-person visit determined by study staff, based on need, for an additional arterial tonometry procedure and blood pressure check.

Dietary intervention: Phase 2 of the protocol will begin within 2 weeks of the end of Phase 1, and typically will begin immediately (i.e., as part of the week 4 visit). During this period, participants will be placed back on their prior antihypertensive therapy, if any, under [name] guidance. Prior to the first Phase 2 visit, subjects will be randomized to control (motivational interviewing only) or the addition of the WHEELS-I program. At the first visit of Phase 2, participants will update their cognitive representation of the DASH/SRD, and have an inperson dietitian session during which motivational interviewing techniques will be employed to explore and support willingness to change dietary habits. If the participant desires, the motivational interviewing portion of the visit may be conducted by telephone. Motivational interviewing-based counseling will continue via telephone during week 2, month1 visit, and at months 2 and 4.

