The remainder of the outcomes are *Phase 2*-related, i.e. intended to determine longer-term effects of dietary change between the WHEELS and non-WHEELS groups, with both receiving motivational interviewing-based dietary counseling. The primary outcome of *Phase 2* was the change in left ventricular mass index (LVMI, using the Devereaux and Dubois formulas for left ventricular mass and body surface area, respectively) by echocardiography, with secondary outcome of change in PWV, between baseline and end of study participation. These outcomes were assessed using linear regression adjusted for baseline value. Key additional pre-specified outcomes were the change in DASH/SRD adherence measured both by 3-day food diary and Food Frequency Questionnaire (FFQ) and the change in clinic systolic and diastolic blood pressure (BP), between baseline and end of study participation. These were measured using generalized estimating equations to account for repeated within-subject measures over time (baseline/2 weeks and at 1 and 6 months of *Phase 2*) and interaction with WHEELS treatment group assignment. Other pre-specified outcomes were changes in serum triglycerides and urine sodium:potassium ratio between baseline to the end of study, evaluated using 2-sample t-testing.

The sample size for *Phase 2* was set by the participants completing *Phase 1* and influenced by drop-out during the 6 months of the interventions to promote DASH/SRD adoption. We assumed that an additional 10% of subjects will drop out during *Phase 2*, resulting in 90 subjects with evaluable data. The sample size was estimated based on anticipated effects on DASH/SRD adherence, the presumed primary driver of cardiovascular and BP changes in the study. Based on national survey data and our preliminary work, we expected the mean baseline DASH/SRD adherence score by 3-day food diary to be 2.5 ± 1.5 points (scale, 0-9). A sample size of 90 provides >80% power to detect an intra-group change of 0.6 between baseline and the end of study, based on paired t-testing two-sided Type I error of 5%. This sample size provides >80% power to detect a differential between group change in dietary score of 0.9, based on a two-sample t test and two-sided Type I error of 5%.

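### Phase 2 BP, PWV and LVMI changes measured from Week 2 run from off-drug to on-drug, so within-group changes and the salt-sensitivity contrast mix drug restart with diet; the randomised WHEELS contrast is protected

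*Protocol*

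**What the plan says.** **Drug status.** The protocol's Phase 1 study design sets a two-week usual-diet period "during which antihypertensive medications, with the exception of calcium channel blockers, will be weaned off"; the Week 2 visit closes that period. Under Phase 2, Dietary intervention, the protocol says that Phase 2 "will begin within 2 weeks of the end of Phase 1, and typically will begin immediately", and that around this transition "participants will be placed back on their prior antihypertensive therapy, if any".

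**Outcomes.** In the protocol (Phase 2 study design) the primary cardiovascular outcome is the "change from baseline (Week 2 visit) to 6 months in left ventricular mass index", compared between salt-sensitive and salt-resistant participants. PWV, left atrial volume index and 24-hour mean BP are key secondaries. The SAP compares the WHEELS and non-WHEELS groups. LVMI is its Phase 2 primary outcome, "with secondary outcome of change in PWV, between baseline and end of study participation". Clinic systolic and diastolic BP are modelled by generalised estimating equations for "repeated within-subject measures over time (baseline/2 weeks and at 1 and 6 months of" Phase 2, with a WHEELS interaction.

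**Adjustment.** The SAP adjusts LVMI and PWV for the baseline value only. The protocol's Phase 1 analysis plan, reused for Phase 2, gives age, race, body mass index, diabetes and kidney function as examples of covariates. The Phase 2 analysis plan adds dietary concordance and change in 24-hour BP. No model names antihypertensive withdrawal or use, although the History and exam section has medications updated at every visit.

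**The concern.** A change score attributes to the study period whatever differs between its two ends. Here one planned difference is the drug regimen. The protocol's own background links hypertension to left ventricular hypertrophy and stiffer arteries, so restarting antihypertensives cannot be assumed neutral for BP, PWV or LVMI.

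Two kinds of result are exposed. First, a within-arm change or a time effect could show a fall that diet did not cause. The SAP calls dietary adherence the presumed main driver of cardiovascular and BP change, so a dietary reading would come easily. Second, salt-sensitivity status is not randomised. If one phenotype had more drugs withdrawn and restarted, its Week 2 to Month 6 change would differ for that reason alone.

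The planned adjustment for change in 24-hour BP does not solve this. That variable contains both the drug and the diet effect, so conditioning on it would also remove the part of the diet effect that acts through BP.

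**Working it through.** **1. The plan's own figure.** Phase 2 assumes 90 evaluable participants, a between-group difference of 0.9 in dietary score and an SD of 1.5. The effect size is 0.9/1.5 = 0.6. With 45 per group, power is 0.804 by the two-sample t test (0.812 by normal approximation), so the stated >80% is reproduced. The same effect size is used for LVMI. This point does not depend on that figure.

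**2. Visits against drug status** (protocol, Figure 8 and the sections cited above).

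| Measure | Before the wean | Week 2, after the wean | After restart |
|---|---|---|---|
| Clinic BP | Screening | Yes | Months 1 and 6 |
| 24-hour BP | None | Yes | Months 1 and 6 |
| PWV | None | Yes | Month 6 |
| LVMI | None | Yes | Month 6 |

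For the last three measures the only possible study baseline falls after the wean. For clinic BP a screening value exists, and the SAP does not say which visit supplies the baseline.

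**3. Within-group change with no dietary effect.** The documents give neither the share *f* who restart nor the systolic effect *b* of restarting. Assume *f* = 0.6 to 0.9 and *b* = 3 to 10 mmHg.

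- Mean fall = *f* × *b*: 0.6 × 3 = 1.8 mmHg to 0.9 × 10 = 9.0 mmHg.
- For scale, the preliminary WHEELS-I data show falls of 9 mmHg at 30 days and 8 mmHg at 90 days.
- The 90-day change SDs in those data are *s* = 13 and 17 mmHg. The standardised shift is *fb* / √(*s*² + *f*(1−*f*)*b*²).
- Low end: 1.8/√(289 + 2.16) = 0.105. High end: 9.0/√(169 + 9) = 0.675.
- With 45 in a group, a paired two-sided 5% test is then significant in about 11% to 99% of trials, instead of 5%.

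**4. Salt-sensitive against salt-resistant.** Assume that the share restarting differs by 10 to 30 percentage points and that the effect is 5 to 10 mmHg.

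- Bias = difference in share × effect: 0.1 × 5 = 0.5 mmHg to 0.3 × 10 = 3.0 mmHg.
- With 45 per group and a change SD of 15 mmHg, a nominal 5% test rejects in 5.3% to 15.5% of trials.

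**5. WHEELS against non-WHEELS.** Randomisation makes the expected restart effect equal in both arms, so the expected shift is 0. What remains is extra variance. With 80% restarting at 10 mmHg, restart adds an SD of 10 × √(0.8 × 0.2) = 4 mmHg.

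- √(13² + 4²)/13 = 13.60/13 = 1.046.
- √(17² + 4²)/17 = 17.46/17 = 1.027.

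The standard error rises by about 3% to 5%, which is the most that adjustment could recover under these inputs.

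The documents give no basis for a corresponding PWV or LVMI figure, so none is offered.

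**The case against.** The strongest reply is that the SAP's Phase 2 inference is the randomised comparison. Both arms restart, and the BP model tests the interaction with WHEELS assignment. This stands. A reader might infer that the WHEELS result is biased; the documents do not support that.

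Second, intra-group inference is planned explicitly only for the dietary score, which drug restart should not move directly. Neither document says that a within-arm BP or PWV fall will be credited to diet. This also stands. The risk lies in how such changes would be read, and nothing in the plan guards against it.

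Third, the SAP uses salt-sensitivity as the comparator only in Phase 1. The Phase 2 salt-sensitivity contrast is in the protocol alone, where the covariate list is open-ended. The documents do not show that drug burden differs by phenotype. So the confounding is possible, not demonstrated, and matters only if that contrast is reported.

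Fourth, a reader might conclude that the clinic BP baseline is Week 2 and that the screening value goes unused. The SAP's wording does not settle this. The same sentence covers the food frequency questionnaire, taken at screening, and the food diary, taken at Week 2. If screening supplies clinic BP, the off-drug to on-drug problem does not arise there in the same way. PWV, LVMI and 24-hour BP have no such alternative.

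Finally, making screening BP the main baseline is not clearly better. It comes from one visit, it is truncated by the 160 mmHg entry limit, and it invites regression to the mean.

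**Conclusion.** The point holds in limited form. For participants who stopped a drug, within-group and time effects from Week 2 in PWV, LVMI and 24-hour BP combine drug restart with diet. So do those in clinic BP, if Week 2 is its baseline. Participants on no antihypertensive, or only on calcium channel blockers, are unaffected; their share is not given. The Month 1 part concerns BP only, because PWV and LVMI are not measured then.

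Under the stated assumptions the spurious systolic fall is 1.8 to 9.0 mmHg within a group, and the possible bias is 0.5 to 3.0 mmHg in the salt-sensitivity contrast. These ranges illustrate scale and are not estimates from the documents. The WHEELS contrast is unbiased in expectation and loses only a little precision. Unequal drug adjustment later in Phase 2 could still affect it, since the Safety Monitoring section allows such adjustment.

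**What to change.** 1. **Covariate.** Add the number of antihypertensive classes withdrawn before Week 2 to the Phase 2 BP, PWV and LVMI models. Do this for the WHEELS contrast, and for the protocol's salt-sensitivity contrast if it is reported. In the repeated-measures BP model, enter it with its interaction with visit; a main effect alone would not account for a change over time. It is fixed before randomisation. Drug status at follow-up may be affected by assignment, so use it only in a sensitivity analysis, and tabulate drug status by visit.
2. **Interpretation.** Label within-group Week 2 to Month 6 changes in BP, PWV and LVMI as diet plus drug restart. Rest Phase 2 conclusions about the dietary intervention on the randomised contrast.
3. **Clinic BP baseline.** State which visit supplies it. Show the change from the on-treatment screening value as a sensitivity analysis, with its limits noted: a single visit, the 160 mmHg entry limit and regression to the mean.

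The cost is SAP wording and one covariate from data already collected. A class count is a crude proxy for drug effect, and within-group claims become weaker. The SAP describes its analyses in the past tense. If results have already been seen, date these additions, mark them as post hoc, and show the planned results beside them. No change to drug handling is proposed.
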